(3) Is the *improvised dressing* culturally acceptable to health care providers, patients, and families for managing SCLUs in Jamaica?

The expected study outcome is improvised dressing superior effectiveness and quality of life, when compared with usual practice, without increased safety and acceptability issues.^{13,59,60,62} The improvised dressing is likely to be the least expensive choice, with the added benefit of being available as first aid treatment throughout Jamaica. The advanced dressing is likely to be more expensive with respect to materials costs, although fewer dressing changes are anticipated and pain medication expenses are likely to be reduced. Based upon the review of the literature, no serious infections or other safety issues are anticipated for any group. However, to ensure that complications are not overlooked, in addition to the onsite researchers' vigilance, weekly wound photos will be assessed for complications (signs of infection, wound deterioration, or clinically relevant maceration) by two off-site blinded wound experts, Drs. [name] and [name].

Definitions:

Sickle cell leg ulcer – a wound in a HbSS or HbS β^0 positive patient, open greater than one month,⁷ below the level of the knee excluding the plantar surface of the foot.

Closed wound -100% epithelialized with no discernible scab or exudate production (paper napkin remains dry when lightly pressed against area, and no recurrence in the subsequent two weeks)

Safe – infection and other complications (healing-impairing maceration, keloid, and contracture rates) not statistically significantly higher than usual practice, with no major adverse events attributable to the method

Effective – ulcer closure rates or ulcer surface area reduction rates not statistically significantly lower than usual practice

Acceptable – average acceptability scores of 4 or higher on a 1-5 scale

3. Methods and Materials

a. Study design

This study will be a targeted-blinded (the off-site wound experts and the local physicians verifying wound closure and/or complications will be blinded to the randomization group), randomized controlled trial with three arms: (1) usual practice (negative control), (2) the improvised dressing, and (3) the advanced dressing (positive control). The expected outcome is improvised and advanced dressing superiority.

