Decrease in SCLU surface area will be used to answer research question 1. Conducting a power analysis for this study is challenging because only one study of SCLUs has demonstrated a statistically significant outcome, and the effect size was obscured by high standard deviations, which is a common problem in studies of wounds.⁸ Improvised plastic dressings similar to the study dressings were used in 49 chronic pressure ulcers in elderly patients, which are often slow to close, if they heal at all.⁶⁰ These two studies demonstrated a significant difference with confidence intervals of 99% with ~25 patients per group. Based upon these sample sizes and the Central Limit Theorem, it is reasonable to set the minimum sample size for this study at 30 patients per group,.^{88,89}

d. Variables

Dependent Variables (measured weekly - tools and permissions in appendices):

- 1. Persistent wound pain (using the Faces Pain Scale Revised (FPS-R))
- 2. Procedural (dressing change) wound pain
- 3. Amount of pain medication taken, including a total number of morphine equivalents plus non-opioid pain medications
- 4. Approximate time spent standing, or sitting with leg dependent without compression (estimated hours per week)
- 5. Patient overall quality of life (assessed with the ASCQ-Me Emotional, Pain, Social Functioning, Stiffness, and Sleep Impact Short Forms)
- 6. Patient wound-specific quality of life (assessed with the Wound QoL tool)
- 7. Materials costs (estimated, using lowest retail costs on Amazon.com for items not on the UWI price sheets)
- 8. Time spent performing dressing changes
- 9. Wound complication rates (e.g., wound infection, healing impairing maceration, wound deterioration)
- 10. Change in wound surface area (measured in cm² electronically using software that automatically corrects for skew, such as HealthEPix or WoundMatrix)⁹⁰

Dependent Variables (measured one time, at graduation from study)

- 11. Wound closure time, in weeks (see definitions; verified two weeks later. Omit patients whose wounds did not fully close they are included in 10., above.)
- 12. Acceptability of dressing choice patient (5 point Likert scale and qualitative free response)
- 13. Acceptability of dressing choice family member (5 point Likert scale and qualitative free response)
- 14. Acceptability of dressing choice UHWI staff (5 point Likert scale and qualitative free response)

Independent Variables (documented at initial study visit):

1. Patient gender

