Patients (and adult relatives of eligible patients under the age of 18) will have the study explained to them by one of the members of the UHWI surgical team. Questions will be addressed thoroughly. Families will be assured that if they choose not to participate in the study, the SCLU will be managed with usual practice. The patient (and a decision-maker of the family, in the case of a minor) must sign the consent for the patient to be enrolled in the study.

Immediately after consent is obtained, the study tools (Patient Data Collection sheet, Faces Pain Scale – Revised (FPS-R), ASCQ-Me, and Wound QoL) will be explained to the patient and family. Baseline persistent pain will be assessed using the Faces Pain Scale – Revised (FPS-R).

All of the initial independent variable data will be handwritten onto the patient's individual Study Data Collection Form upon enrollment in the study. The largest SCLU upon initial presentation is the study wound. All SCLUs will be measured for the first four weekly visits to UHWI. If two or more SCLUs in close proximity join during the first four weeks, the sum of the initial areas will be the initial wound size.

The SCLU(s) will be measured initially by placing two pieces of clear plastic on top of one another and tracing the wound edges. The plastic that came in contact with the wound(s) will be discarded and the plastic with the markings on it will be added to the patient's documentation so that the patient can be shown if the SCLU is becoming smaller at subsequent dressing changes. SCLU area will be measured in cm² electronically from a photo, using software such as HealthEPix or WoundMatrix.

Patients (with the support of their families) will be taught to evaluate and document persistent and dressing change pain, pain medication doses taken, time spent and supplies used at dressing changes, their activity, and their use of compression on a checklist-style Study Continuation Form daily. They will either provide the research team with their weekly summary and wound photo via WhatsApp, or they will attend the clinic weekly so that the research team can obtain this data. Two encrypted USB drives containing the data, including wound photographs, will be updated weekly on an alternating schedule and stored in a securely locked file in the UHWI surgical clinic dressing area, along with the paper study documentation.

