Weekly, de-identified photographs will be sent by the Principal Investigator to be viewed by two blinded wound experts ([name] and [name]) off site. If the blinded experts, or anyone else involved in the study, expresses concern that a patient is exhibiting signs of possible infection, maceration that is delaying healing, or wound deterioration, a physician at UHWI or the SCU who is not otherwise involved in the study will be asked to evaluate that patient. The patient's dressings will be removed prior to this evaluation so that their treatment group will not be revealed to the physician (the evaluation by the physician is thus blinded to treatment group). If the physician determines that the patient's condition has not improved with the prescribed treatments (e.g., antibiotics), the patient will be withdrawn from the study. Any

patient who transitions out of the group to which they were randomized for any reason will receive usual treatment for their ulcer for the remainder of their 12 week study period.

When the treatment personnel at UHWI or the blinded remote observers state that the patient's wound appears to be closed, a physician at UHWI or the SCU who is not otherwise involved in the study will be asked to evaluate that patient. The patient's dressings will be removed prior to this evaluation so that their treatment group will not be revealed to the physician. Wound closure is defined as 100% epithelialized with no discernible scab or exudate production (a paper napkin blotting the area remains dry). Patients will be reassessed two weeks later to verify that the wound was truly closed and did not immediately recur.

Patients who are diagnosed with wound closure or have completed the 12 week study period will be taken aside privately and asked to rate the acceptability of their treatment using a 5 point Likert Scale. A family decision-maker will also be privately asked to rate the acceptability of the treatment. One of the research team members will enter this basic acceptability data for the patient and the family on the patient's Data Collection Tool. At that point, the patient will graduate from the study. However, patients and families will be instructed to return to UHWI for follow-up if a complication or recurrence develops. Any delayed complications (e.g., recurrence within 3 months) will be recorded on the patient's Data Collection Tool by the nurse or physician to whom the patient reports it.

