The patients, and available adult relatives of all eligible patients ages 13 to 18, will have the study explained to them by a member of the research team. Questions will be addressed

thoroughly. Patients and families will be assured that if they choose not to participate in the study, their SCLUs will be treated with usual practice. The patient, and in the case of a participant under the age of 18, a parent or guardian, must sign the consent for the patient to be enrolled in the study. Students will be accommodated after school or on a Saturday.

Time required to complete the weekly assessments for the study will create a burden for the study participants (approximately 30 minutes per week, total, and half a day once a month when patients come to UHWI in person for evaluation). However, dressing changes for the two comparator dressings are expected to be less painful and less time consuming than usual practice. In addition, all participants will be given study dressings and their wound care will be provided free of charge. Further, all study participants will be give a zipper bag of the dressing materials of their choice (gauze, plastic bags, or PolyMem; plus a roll of tape and a roll of stretch gauze) at the conclusion of the study.

This study is a collaborative project between the UHWI surgical team and the [name] research team. In addition to her role as an independent researcher for tropical developing countries, as is stated in Ethics Checklist, [name] is an employee of Ferris Mfg. Corp., makers of PolyMem Dressings. This research study falls under her role as Charity Liaison for this company. The study has been designed with a high degree of rigor to help ensure that the results will not be biased as a result of this relationship.

The researchers anticipate that what is learned from this study can directly benefit the urbandwelling Jamaican participants. In addition, many participants will benefit indirectly from the knowledge that their participation in the study can contribute to improving the lives of wound patients living in the rural areas.

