SCLUs are often disabling, scarring, and exquisitely painful. The research literature suggests that both the improvised dressing and the advanced dressing can decrease pain. The advanced dressing has also been shown to decrease scarring. However, children ages 13 - 18 are an especially vulnerable population. They are included in the study because this is the peak age group for SCLU formation, and therefore they are the most likely to benefit if the results can be generalized to them.¹⁵

5. Limitations

Blinding is a challenge inherent to studies of wounds. Although the the healthcare professionals who will monitor and verify wound closure and complications (outcomes) will be blinded, it is not possible to blind the participants or the research team members, because they will provide the wound management in this study.

Despite the incentives to remain in the study (phone cards monthly and wound management supplies at the conclusion of the study), it is possible that there will be a substantial dropout rate, because it is easy for patients with SCLUs to become discouraged, and they may feel that they have derived the major benefits of joining the study after the first few weeks.

All of the published studies of improvised dressings describe wound care performed by health professionals based in urban hospitals or long term care facilities. Although this study will be conducted in a tropical outpatient setting, it too is being conducted by health care professionals in an urban area. Also, Jamaica is significantly more developed than many of the countries for whom the improvised dressing educational program may be beneficial. Therefore, this study may not uniformly generalize to rural areas of tropical developing countries, where health professionals are absent.

6. Acknowledgments:

The researchers would like to thank all participants in the study.

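### Ulcer area, which answers question 1, is not among the outcomes assessed blind, so the plan as written permits unblinded outlining of wound edges

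*Combined protocol and SAP*

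**What the plan says.** **Role of area.** Section 3c states: "Decrease in SCLU surface area will be used to answer research question 1". The definitions in section 2 make area one of two routes to effectiveness: "ulcer closure rates or ulcer surface area reduction rates not statistically significantly lower than usual practice".

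**How area is obtained.** Section 3d lists it as weekly variable 10: "Change in wound surface area (measured in cm² electronically using software that automatically corrects for skew, such as HealthEPix or WoundMatrix". Section 3h adds: "SCLU area will be measured in cm² electronically from a photo, using software such as HealthEPix or WoundMatrix". Neither section says who draws the wound edge or whether that person knows the arm.

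**Who is blinded.** Section 3a limits targeted blinding as follows: "the off-site wound experts and the local physicians verifying wound closure and/or complications will be blinded to the randomization group". Section 3h gives the off-site experts their material: "Weekly, de-identified photographs will be sent by the Principal Investigator to be viewed by two blinded wound experts". Their listed tasks there and in section 2 are to look for infection, deterioration and maceration, and to flag apparent closure. Section 5 again names only closure and complications as blinded outcomes.

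**Who is not blinded.** Section 5 says "it is not possible to blind the participants or the research team members", since they provide the wound care. Section 3h has the research team obtain the weekly data.

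**Interests.** Section 4 discloses that one researcher "is an employee of Ferris Mfg. Corp., makers of PolyMem Dressings", the arm 3 product.

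**The concern.** Patients and treating staff know the arm, so protection against assessment bias has to come from blinded readers. The plan provides such readers for closure and complications but does not extend them to area.

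Placing the edge of an open ulcer on a photograph is a judgement. The plan says that the software corrects for skew. It does not say that edge detection is automatic, and it leaves the product open. If the person drawing the edge knows the arm and expects one dressing to do better, small consistent differences in where the line falls go straight into the area comparison, and a larger sample does not remove them.

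The literature review in section 1a describes a ten-year plastic-wrap trial in which a blinded observer assessed area reduction from photographs, and calls that trial well designed. The same arrangement is within reach here.

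**Working it through.** **1. The plan's own figure.** Section 3f plans 90 evaluable patients (about 30 per group) and up to 120 recruited to allow for 25% dropout: 90 / (1 − 0.25) = 120. This reproduces. The 30 per group is not derived from an effect size or SD for area, so any SD used below is an assumption.

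**2. Outcomes set against assessors.**
- Closure: flagged by clinic staff or the off-site experts, then verified by an uninvolved physician with the dressing removed (3h). Verified blind.
- Complications: photographs screened by the off-site experts, then evaluated by an uninvolved physician (section 2, 3h). Assessed blind.
- Area: electronic, from a photograph (3d, 3h). Assessor not named, blinding not stated.

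The experts' check for deterioration is a safety screen and yields no area value.

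**3. Does blinded closure fill the gap?** Only in part. Section 3f says that closure is not expected in every patient. Section 3d drops unclosed wounds from closure time (variable 11) and refers them to variable 10. Area therefore carries the effectiveness information for ulcers that stay open, and the definition of effective can be met on area alone.

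**4. When would outlining cause bias?** Let the outcome be ln(area at follow-up) − ln(area at baseline). A reader who always draws the edge too wide by the same factor adds the same constant to both terms, and it cancels. Section 3h describes the initial measurement before randomization. Bias therefore needs outlining that differs by arm after baseline. If follow-up areas in one arm are drawn smaller by a fraction b, the between-arm difference shifts by ln(1/(1 − b)).

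**5. Illustration.** Inputs: 30 per arm (3c, 3f); two-sided 5% test, from the 95% CIs in 3i; SD of log area change 0.7 (assumed); b = 10% (assumed). Normal approximation, no true difference.
- Standard error = 0.7 × √(2/30) = 0.7 × 0.258 = 0.181
- Shift = ln(1/0.9) / 0.181 = 0.105 / 0.181 = 0.58 standard errors
- Type I error = P(|Z + 0.58| > 1.96) ≈ 0.084 + 0.006 = 0.090

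Range over assumed inputs:
- b = 10%: 13% at SD 0.5, 9% at SD 0.7, 7% at SD 1.0.
- b = 20%: 41% at SD 0.5, 24% at SD 0.7, 14% at SD 1.0.

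In SD units, with standard error √(2/30) = 0.258, a shift of 0.1 SD gives 6.7% and a shift of 0.2 SD gives 12.1%.

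These figures cover the 95% superiority comparison only, not the 80% CI fallback in 3i.

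**The case against.** **The plan is silent rather than wrong.** Area measurement is written in the passive with no assessor. A reader might infer that unblinded staff will outline the wounds. The documents do not say so, and 3d refers to appendices on tools that are not in the public text. This stands: the point is what the plan permits. If a blinded procedure exists in an appendix, it only needs stating in 3a and 3h.

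**Question 1 has other blinded support.** A reader might infer that the trial's effectiveness conclusion has no blinded basis. That goes too far. Closure is an alternative criterion and is verified blind, and so are the complications that decide safety.

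**The team is not alone with the photographs.** The off-site experts view them weekly, and section 3h lets some patients and families take and send them. This stands, and it makes the fix easier.

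**The commercial link is narrower than it looks.** A reader might infer that the employed researcher measures area, or has a stake in the improvised dressing. The documents support neither. The interest lies in arm 3, so it bears on comparisons with arm 3. The comparison of the improvised dressing with usual practice does not involve that product.

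**The percentages are hypothetical.** This also stands. No document gives an SD of area change or an outlining error. The figures show sensitivity and do not estimate bias.

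**Blinded reading has limits.** The experts see photographs week by week, so visit order cannot be hidden from them without a separate later reading. Zinc oxide paste around the wound may identify arm 2. These points shape the fix but do not justify leaving area outside the blinded assessments.

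**Conclusion.** The point holds as a cheap improvement. The outcome chosen to answer question 1 is not among those the plan says are assessed blind, its assessor is unnamed, and the team collecting the weekly data knows the arm. Followed as written, the plan allows unblinded outlining.

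Bias is possible, not shown. It would need arm-dependent outlining after baseline, and its size cannot be obtained from the documents. The rise from 5% to about 9% rests on the assumed SD of 0.7 and the assumed 10% difference. The design point does not depend on either value.

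**What to change.** - **Sections 3a and 3h:** add area to the blinded assessments. State that the value analysed as variable 10 is outlined on the coded, de-identified photograph by one of the two off-site experts who already receive it, blinded to arm. Blinding to visit order is not required.
- **Photographs:** where possible, frame or crop them so that dressing material and periwound paste do not reveal the arm.
- **Schedule:** keep variable 10 weekly. If the reading load is to be reduced, amend 3d to name the visits whose area is analysed, so that the two sections agree.
- **Staff tracings on plastic:** state that they serve only to show patients their progress.

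**Cost.** A few protocol sentences and extra reading time, with no new staff and no change in sample size. The upper limit for one outline per patient at baseline and at each of 12 weeks is 120 × 13 = 1,560 outlines, fewer with dropout and early closure. Four named visits would need at most 120 × 4 = 480. Blinding would remain imperfect wherever paste residue is visible.

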Sickle cell leg ulcers (SCLUs) are a challenging chronic wound type whose sufferers could benefit from a more economical, less painful, dressing option.^{8,9} Only one of the studies involving occlusive plastic improvised dressings took place in a tropical environment, and this study tested a sterile drape placed in an operating theater on surgical wounds (donor sites).⁵⁸ Although theoretically autolytic debridement should keep wounds dressed with plastic bags clean, in practice there are concerns that wound infections could be problematic, because tropical climates are known to promote increased microbial growth.¹⁹ Therefore, it is prudent to test the plastic bag dressing protocol under the guidance of health care professionals, where sufficient numbers of patients can be enrolled at a single site to answer the study questions definitively.

UHWI (the University Hospital of the West Indies) provides a rare intersection of sufficient research expertise to obtain accurate data, and a large number of SCLU patients living in a true tropical climate (air conditioning is not pervasive), allowing for partial testing of the ecological validity of improvised dressings. Validating the safety and effectiveness of affordable dressing materials would vastly improve treatment outcomes by winnowing out harmful self-care choices and supporting the beneficial choices. It would also empower patients, their families and lay health care providers by enabling them to implement effective treatments as first aid, prior to their arrival at an outpatient clinic or hospital.

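### Unblinded staff can add referrals to the blinded physician, so the confirmed complication counts behind 'Safe' can differ by arm through unequal referral

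*Combined protocol and SAP*

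**What the plan says.** Section 3h of the combined protocol and SAP gives two routes to the physician who confirms an outcome with the dressing removed.

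- **Complications.** The trigger is "If the blinded experts, or anyone else involved in the study, expresses concern that a patient is exhibiting signs of possible infection", or maceration that delays healing, or deterioration.
- **Closure.** The trigger is narrower: "When the treatment personnel at UHWI or the blinded remote observers state" that the wound appears closed. The physician then examines the wound, and a recheck follows two weeks later.

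One of these routes is blinded and covers every arm: "Weekly, de-identified photographs will be sent by the Principal Investigator to be viewed by two blinded wound experts". The other is not. Section 5 (Limitations) says "it is not possible to blind the participants or the research team members, because they will provide the wound management in this study". Section 2 (Research Questions/Aim) relies on both routes: "in addition to the onsite researchers' vigilance, weekly wound photos will be assessed for complications".

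Section 5 also says that the "healthcare professionals who will monitor and verify wound closure and complications (outcomes) will be blinded". Section 3a (Study design) limits blinding to the off-site experts and the verifying physicians.

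The definitions in section 2 call a dressing safe if infection and other complication rates are not statistically significantly higher than under usual practice. Effective means that closure rates or area reduction rates are not significantly lower. Section 3c (Sample) names surface area as the measure for research question 1.

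**The concern.** A blinded physician can reject a false alarm but cannot find a complication that nobody refers. If on-site staff watch one arm more closely than another, the confirmed counts differ even when the true rates are equal and every confirmation is properly blinded.

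The plan contains possible reasons for unequal attention. Section 1b (Rationale) says of plastic-bag dressings in the tropics that "there are concerns that wound infections could be problematic". Section 3a expects the improvised and advanced dressings to be superior. Section 4 (Ethical Considerations) discloses that a member of the research team is employed by the maker of the advanced dressing. These reasons do not all point the same way, so the direction of any bias is unknown.

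The safety conclusion is at stake. Fewer staff referrals in the improvised arm would favour a finding of safe, and more would count against it. The plan does not record who raised each concern, so the question could not be settled afterwards.

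**Working it through.** **Step 1: which events depend on unblinded referral?** Section 3e lists smell and raised warmth around the wound among the clinical signs of infection. A photograph shows neither, so for these signs the staff route is the only one. Visible signs have both routes. Section 3h sets no objective referral threshold, no scheduled physician evaluation of every patient, and no log of referral source.

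**Step 2: group size.** Section 3f gives about 90 patients, or 30 per group. Its recruitment cap reproduces: 90 / (1 − 0.25) = 120. The documents give no complication rate, photo sensitivity or staff referral rate, so everything below is assumed.

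**Step 3: model.** Let *p* be the true complication risk, equal in both arms. Let *s* be the share caught by the blinded photo experts, also equal. Let *u* be the share of the remainder that staff refer, which may differ by arm. All referred true events are taken as confirmed.

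Observed rate = *p* × [*s* + (1 − *s*) × *u*]

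**Step 4: moderate imbalance, *p* = 20%, *s* = 60%.**

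- *u* = 0.8 v 0.4: 0.20 × (0.6 + 0.4 × 0.8) = 18.4%, against 0.20 × (0.6 + 0.4 × 0.4) = 15.2%. The ratio is 1.21. Per 30 patients this is 5.52 v 4.56, a gap of 0.96.
- *u* = 0.9 v 0.3: 0.20 × (0.6 + 0.4 × 0.9) = 19.2%, against 0.20 × (0.6 + 0.4 × 0.3) = 14.4%. The ratio is 1.33. Per 30 patients this is 5.76 v 4.32, a gap of 1.44.

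Exact enumeration of a two-sided 5% pooled z test with 30 per arm gives false-positive rates of 0.063 and 0.079, against about 0.05 with equal referral. Under Fisher's exact test they are 0.026 and 0.035.

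**Step 5: range, *p* = 30%, 30 per arm, same z test.**

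| *s* | *u* | Expected confirmed cases | False-positive rate |
|---|---|---|---|
| 60% | 0.8 v 0.4 | 8.3 v 6.8 | 0.070 |
| 60% | 0.9 v 0.1 | 8.6 v 5.8 | 0.137 |
| 50% | 1 v 0 | 9.0 v 4.5 | 0.281 |
| 80% | 1 v 0 | 9.0 v 7.2 | 0.080 |
| 100% | any | 9.0 v 9.0 | 0.049 |

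Over *p* = 20–40% and *s* = 50–80%, the rate runs from about 0.05 to 0.39. The top end needs staff to refer every missed event in one arm and none in the other. If only the blinded experts trigger evaluation (*s* = 60%), or if everyone is evaluated, the rate is about 0.049 to 0.055.

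**Step 6: closure.** A closed wound stays visible in the next weekly photo, and a premature call must pass the physician's examination and the two-week recheck. Unequal referral therefore mainly moves the closure date, by about one photo interval, and could change a count only near week 12. The model in step 3 treats each event as a single chance of detection, so it should not be applied to closure counts.

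**Step 7: surface area.** It is measured weekly for all patients without any referral.

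**The case against.** The strongest reply is that the weekly blinded photo review already covers all arms, and nothing in section 3h lets staff overrule it. That stands. A reader might infer that unblinded staff decide who reaches the physician, but the text lets them only add referrals. The wording that admits anyone in the study applies to complications and not to closure.

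The size is also open to challenge. If 60% is the chance of detection per weekly photo, a sign visible for two weeks is caught with probability 1 − 0.4² = 84%. The rates then become 0.20 × (0.84 + 0.16 × 0.8) = 19.4% and 0.20 × (0.84 + 0.16 × 0.4) = 18.1%, a ratio of 1.07. This is fair for lasting visible signs. It does not help with smell or warmth.

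The motive is inferred. Section 1b's concern about infection explains why the method is tested under professional guidance and does not tell staff to watch one arm. Section 2 anticipates no serious infections in any group. This leaves the direction unknown, which is a reason to record referral source.

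A reader might also take section 5 to misstate the blinding as a whole. It does not: the same sentence discloses that the research team is unblinded, and the photo experts do monitor blinded. The mismatch is confined to the word for monitoring, because on-site staff monitor and refer too.

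**Conclusion.** The point holds for complications. Verification is blinded, selection for verification is only partly so, and the counts behind 'Safe' can differ by arm through unequal referral. The size cannot be derived from the documents. Under the moderate assumptions it is about 1 to 1.5 patients between arms of 30, with a small rise in the false-positive rate. Larger figures need extreme imbalance or poor photo detection.

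The documents do not support two stronger readings. One is that closure counts are exposed to the same degree. Closure persists and must pass a blinded examination and a recheck, so mainly its date is at risk. The other is that the effectiveness result as a whole is compromised. Surface area is not gated by referral, and 'Effective' can be met through it.

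**What to change.** 1. Keep staff referral for patient care exactly as it is.
2. Have the two blinded experts record a flag for every weekly photo (complication yes/no, closed yes/no), whether or not staff have already referred the patient. Record the source of every referral. A field showing only who raised the concern first would not do: vigilant staff would pre-empt the experts and remove events from that arm's expert count.
3. Date the counted closure from the first expert-flagged photo that is then confirmed by the blinded physician and the two-week recheck.
4. Report the between-arm complication comparison for expert-flagged confirmed events (flagged at any time) beside all confirmed events, each with its 95% CI. Call the dressing safe only if both support it.
5. Reword section 5 to match section 3a: the off-site experts and verifying physicians are blinded, and the on-site staff who also monitor and refer are not.

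The cost is one or two data fields, some SAP wording, and closure dated up to a week later in all arms. Limits remain. The expert-flagged set has fewer events, so it is easier for it to show no significant excess. It misses signs not visible in photos, and events that staff raise and that resolve before the next photo. The all-source count must therefore stay beside it.
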